## **8.3 Primary Efficacy Endpoint and Analyses**

There are no primary efficacy endpoints or analyses for this study.

## **8.4 Secondary Efficacy Analyses**

Descriptive statistics will be provided for each treatment group for all visits. These include the number of observations, mean with 95% confidence interval, standard deviation, median, minimum and maximum for continuous endpoints; and frequencies and percentages with 95% confidence interval using Wilson score for binary endpoints.

No missing data imputation will be applied. All efficacy analyses will be based on As Observed (AO) analysis, and thus a subject who does not have an evaluation at the primary analysis time point will not be included.

## **8.5 Additional Efficacy Analyses**

No additional efficacy analyses are planned.

## **8.6 Efficacy Subgroup Analyses**

No subgroup analyses will be performed.

## **9.0 Safety Analyses**

### **9.1 General Considerations**

Safety analyses will include reporting of adverse events, laboratory, and vital signs measurements. Safety analyses will be carried out using the Safety Analysis Set.

The following summary statistics will be presented for subjects who have both baseline and post-baseline values for laboratory parameters and vital signs: the mean value at Baseline and at each respective protocol specified visit, and the mean, standard deviation and median for changes from Baseline. Categorical data will be summarized using frequencies and percentages. The number of non-missing values will be given. Missing safety data will not be imputed.

### **9.2 Adverse Events**

Adverse events (AEs) will be summarized and presented using primary MedDRA System Organ Classes (SOCs) and preferred terms (PTs) according to the version of the MedDRA coding dictionary used for the study at the time of database lock. The actual version of the MedDRA coding dictionary used will be noted in the AE tables and in the clinical study report. Specific adverse events will be counted once for each subject for calculating percentages, unless stated otherwise. In addition, if the same adverse event occurs multiple times within a subject, the highest severity and level of relationship to investigational product will be reported.

TEAEs will be summarized using subject data from Study M16-763 and a combination of data from Studies M16-063 and M16-763 that includes any subject receiving a dose in Study M16-763, respectively. Only the datasets from Studies M16-063 and M16-763 that includes any subject receiving a dose in Study M16-763 will be used for per 100 patient years of exposure analyses (for the Study M16-763 study).

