5 STUDY ACTIVITIES

5.1 Eligibility Criteria

Subjects must meet all of the following criteria in order to be included in the study. Anything other than a positive response to the questions below will result in exclusion from study participation.

Consent

- ✔ 1. Subjects or their legally authorized representative must voluntarily **sign and date an informed consent**, approved by an independent ethics committee (IEC)/institutional review board (IRB), prior to the initiation of any screening or study-specific procedures.

Demographic and Laboratory Assessments

- ✔ 2. Subjects have completed Study M16-063 (i.e., the preceding study of ABBV-105 and ABBV-599) and have not developed any laboratory or clinical discontinuation criteria as defined in that study.

Relevant Study M16-063 eligibility requirements applicable to Study M16-763 are as follows:

- a. Subjects or their legally authorized representative must voluntarily **sign and date an informed consent**, approved by an independent ethics committee (IEC)/institutional review board (IRB), prior to the initiation of any screening or study-specific procedures.
- b. Adult **male or female**, at least 18 years old.
- c. **Laboratory values** not meeting toxicity management criteria from the Study M16-063 study:
- d. Diagnosis of RA for ≥ 3 months based on the 2010 ACR/European League Against Rheumatism (EULAR) classification criteria for RA.
- e. No history of any of the following cardiovascular conditions:
 - Moderate to severe congestive heart failure (New York Heart Association Class III or IV).
 - Recent history (within past 6 months) of cerebrovascular accident (CVA), myocardial infarction, and/or coronary stenting.
 - Uncontrolled hypertension as defined by a persistent systolic blood pressure (BP) > 160 mmHg or diastolic BP > 100 mmHg. For subjects with known hypertension, the

subject's BP must be stable for at least 4 weeks on current, stable anti-hypertensive medications.

- Prior unprovoked deep vein thrombosis or pulmonary embolism (PE) (i.e., any spontaneous event not directly attributable to trauma or vascular instrumentation).
 - Any other condition which, in the opinion of the Investigator, would put the subject at risk by participating in the protocol.

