- l. Must not have active TB or meets TB exclusionary parameters (defined as the presence of active TB or latent TB not adequately treated as per protocol requirements).
- m. Must not have used known strong cytochrome P450 (CYP)3A or CYP1A2 inhibitors or strong CYP3A or CYP1A2 inducers from Screening through the end of the study.

- n. Must not have had receipt of any live vaccine within 4 weeks prior to the first dose of study drug, or expected need of live vaccination during study participation including at least 4 weeks after the last dose of oral study drug.
- o. Must not have a history of any malignancy except for successfully treated non-melanoma skin cancer (NMSC) or localized carcinoma in situ of the cervix.
- p. Must not have a history of clinically significant (per Investigator's judgment) drug or alcohol abuse within the last 6 months.
- q. Must not have a history of gastrointestinal perforation (other than appendicitis or penetrating injury), diverticulitis or significantly increased risk for gastrointestinal perforation per investigator judgment.
- r. Must not have any conditions that could interfere with drug absorption including but not limited to short bowel syndrome.
- s. Must not be a recipient of an organ transplant.
- t. Must not have history of clinically significant medical conditions or any other reason that in the opinion of the Investigator would interfere with the subject's participation in this study or would make the subject an unsuitable candidate to receive study drug.
- u. Must not have had an active infection(s) requiring treatment with parenteral anti-infectives within 30 days, or oral anti-infectives within 14 days prior to the first dose of study drug.
- v. Must not have a history of an allergic reaction or significant sensitivity to constituents of the study drugs (and its excipients) and/or other products in the same class.
- w. Subjects must have been treated for ≥ 3 months with ≥ 1 bDMARD therapy but continue to exhibit active RA or had to discontinue due to intolerability or toxicity, irrespective of treatment duration.
- x. Subjects must have been receiving csDMARD therapy ≥ 3 months prior to Study M16-063 baseline visit.

The following csDMARDs are allowed: oral or parenteral methotrexate (MTX) (7.5 to 25 mg/week), sulfasalazine (≤ 3000 mg/day), hydroxychloroquine (≤ 400 mg/day), chloroquine (≤ 250 mg/day), and leflunomide (≤ 20 mg/day).

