7.2 Definition for Analysis Populations

The Full Analysis Set (FAS) includes all subjects who completed Study M16-063 and received at least 1 dose of assigned study drug in Study M16-763. The FAS will be used for efficacy and baseline analyses. Subjects will be grouped according to treatments as randomized for Study M16-063.

The Safety Analysis Set also includes all subjects who completed Study M16-063 and received at least one dose of assigned study drug in Study M16-763. Subjects will be grouped according to treatments actually received in Study M16-763. The Safety Analysis Set will be used for safety analyses.

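### The only planned patient-year rates include about 12 weeks per subject of M16-063 time that entry selection has cleared of deaths and largely of some other events, so those rates understate the extension

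*SAP*

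**What the plan says.** SAP 9.2 plans M16-763-only and combined summaries of treatment-emergent adverse events (TEAEs), but restricts the patient-year analyses to one of them: "Only the datasets from Studies M16-063 and M16-763 that includes any subject receiving a dose in Study M16-763 will be used". SAP 9.2.4 divides TEAEs from both studies by total study drug exposure. SAP 6.0 counts combined exposure from the first M16-063 dose and separately defines an M16-763-only exposure, which no rate uses. M16-763-only events are planned as numbers and percentages.

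Protocol 7.2 defines the safety set as "all subjects who completed Study M16-063 and received at least one dose of assigned study drug in Study M16-763". Protocol 5.1 sets the entry condition: "Subjects have completed Study M16-063 (i.e., the preceding study of ABBV-105 and ABBV-599) and have not developed any laboratory or clinical discontinuation criteria". The same section lists histories that bar entry:
- "Recent history (within past 6 months) of cerebrovascular accident (CVA), myocardial infarction, and/or coronary stenting"
- unprovoked deep vein thrombosis or pulmonary embolism
- gastrointestinal perforation, with exceptions for appendicitis and penetrating injury
- for tuberculosis, "Must not have active TB or meets TB exclusionary parameters"
- for cancer, "Must not have a history of any malignancy except for successfully treated non-melanoma skin cancer (NMSC) or localized carcinoma in situ of the cervix"

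Protocol 7.4 promises rates per 100 patient-years for serious adverse events (SAEs), deaths, adverse events (AEs) leading to discontinuation, and AEs of special interest (AESIs).

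**The concern.** A subject enters these rates only by being dosed in M16-763, yet brings in the whole preceding M16-063 period. Nobody who died in M16-063 can be in the denominator, and subjects who met its discontinuation criteria or had a barred event were not to enter. That time adds patient-years with few or no chances to contribute certain events, which lowers the rate.

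The affected events are among those for which Protocol 7.4 promises rates. The objective is long-term safety, and Protocol 4.2 makes the main comparison with the profile each arm showed in M16-063; a rate that pools the two periods blurs it. Crude M16-763 percentages do not replace a rate when only 20-60% of subjects are expected to complete. The dilution grows as completion falls, so arms with different attrition are diluted unequally.

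**Working it through.** **Inputs from the documents**
- M16-063 time: the extension baseline is Week 12 (Protocol Appendix D), and the top exposure cut-offs in SAP 6.0 differ by 420 - 336 = 84 days.
- Extension treatment: 48 weeks = 336 days.
- Completion: 20-60%, or 40 to 120 subjects (SAP 2.4). Both ends give one base: 40/0.20 = 120/0.60 = 200.
- M16-063 exposure for 200 subjects: 200 x 84/365.25 = 46.0 patient-years (PY).
- TEAE window: up to 30 days after last dose (SAP 9.2.1). Exposure stops at last dose.

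**Assumptions**
- The 200 are extension entrants.
- There are no events of the given type in M16-063 time. This makes the result an upper bound for partly barred categories.
- Attrition is unknown, so three patterns are shown. Mean extension days d are 336 if all complete. With linear attrition, d = 336 x (c + (1 - c)/2), where c is the completion proportion. With all losses at Week 18, d = 336c + 42(1 - c).

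**Arms continuing the same active drug**
- Discontinuations have no post-dose tail: shortfall = 84/(d + 84).
- Deaths and fully barred AESIs, against a constant hazard: shortfall = 1 - (d + 30)/(d + 84) = 54/(d + 84).

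**Pooled active drug, placebo time split off**
- With six equal groups assumed, M16-063 active exposure is 46.0 x 5/6 = 38.3 PY, or 84 x 5/6 = 70 days per extension subject.
- Discontinuations: 70/(d + 70). Deaths and fully barred AESIs: 40/(d + 70).

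| Pattern | d (days) | Extension PY | Disc., continuing arm | Deaths/barred, continuing arm | Disc., pooled active | Deaths/barred, pooled active |
|---|---|---|---|---|---|---|
| All complete | 336.0 | 184.0 | 20% | 13% | 17% | 10% |
| Linear, 60% complete | 268.8 | 147.2 | 24% | 15% | 21% | 12% |
| Linear, 20% complete | 201.6 | 110.4 | 29% | 19% | 26% | 15% |
| Week-18 losses, 60% | 218.4 | 119.6 | 28% | 18% | 24% | 14% |
| Week-18 losses, 20% | 100.8 | 55.2 | 45% | 29% | 41% | 23% |

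Example (assumed count): 10 AE discontinuations in M16-763, pooled active, linear attrition, 60% completion. Combined: 10/(147.2 + 38.3) = 5.4 per 100 PY. M16-763-only: 10/147.2 = 6.8, with exact Poisson 95% limits of 3.3-12.5.

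**If selection is incomplete.** Suppose the M16-063 discontinuation rate is a quarter of the extension rate. In a continuing arm the ratio is (d + 0.25 x 84)/(d + 84) = 0.85 if all complete, 0.79 with Week-18 losses at 60% completion, and 0.66 at 20%. The shortfalls are then 15%, 21% and 34% instead of 20%, 28% and 45%.

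**Window mismatch in an M16-763-only rate.** Counting deaths or AESIs to 30 days after last dose over on-drug exposure alone overstates the rate by 30/d: 9% if all complete, 11-15% with linear attrition, 14-30% with Week-18 losses.

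**Which AESIs are barred (Protocol 5.1 against SAP Appendix B)**
- Nearly fully: active tuberculosis and gastrointestinal perforation.
- Partly: malignancy, since treated non-melanoma skin cancer and cervical carcinoma in situ are allowed; and adjudicated cardiovascular events, since infarction and stroke within 6 months are barred but transient ischaemic attack and unstable angina are not named.
- Little affected: for example, a single non-disseminated zoster episode or a resolved serious infection.
- Not assessable: laboratory AESIs, which depend on M16-063 criteria absent from these documents.

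**The case against.** The strongest reply is that nothing is lost. M16-763-only exposure, event counts and listings of deaths and discontinuations are all planned, so a reader can approximate the missing rate with one division. No test or decision rule uses these rates, and per-group precision is poor. This stands and keeps the severity low. It does not remove a predictable bias in the only rate the plan specifies.

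The discontinuation effect, the largest, depends on what completing M16-063 meant. In M16-763, subjects who stop drug are asked to stay for scheduled visits (Protocol 5.6). If M16-063 did the same, someone could have stopped drug for an AE and still completed. The bar on subjects who met discontinuation criteria makes this unlikely to be common among entrants, but the documents do not settle it. Likewise, if some barred histories were checked only at M16-063 screening, the AESI effect shrinks. The argument for deaths is untouched.

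A reader might infer three stronger things that the documents do not support:
- **All patient-year rates are too low.** Ordinary TEAEs, most SAEs and unbarred AESIs can occur in M16-063 time among subjects who roll over.
- **Every arm is diluted.** SAP 6.0 lists Placebo separately from ABBV-599 After Placebo. If M16-063 placebo time goes to Placebo, the latter arm has no dilution.
- **The planned rate of venous thromboembolism is understated.** Unprovoked events are barred, and Protocol 6.1 lists embolic and thrombotic events as an AESI, but SAP Appendix B has no search for them. There is no planned AESI rate to understate.

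**Conclusion.** The point holds, as a minor one. For deaths, AEs leading to discontinuation (subject to the unseen M16-063 definition of completion) and the AESIs barred at entry, the only planned patient-year rate understates the extension rate. The table gives the size. Its percentages do not depend on the figure of 200, but they do depend on the attrition pattern and on completion among entrants. If the plan's 20-60% refers to a wider base than entrants, completion among entrants is higher and the shortfalls move towards the all-complete row. The 45% end needs 80% of subjects to stop exactly at Week 18. For malignancy and cardiovascular events all the figures are upper bounds. What is missing is a rate and a label, not data.

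**What to change.** In SAP 9.2.4:

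1. Add M16-763-only rates per 100 PY for deaths, AEs leading to discontinuation and the Appendix B AESI categories. Use the M16-763-only exposure in 6.0 and the M16-763-only TEAE definition in 9.2.1, so that counts reconcile with the planned tables. Footnote any death or discontinuation arising from an AE with onset in M16-063. For deaths and AESIs, either count on-drug events only, or add each subject's observed follow-up (up to 30 days) to the denominator. It should be observed time, because Protocol 5.6 makes the follow-up call optional after consent withdrawal.
2. Keep the combined rate, labelled as conditional on completing M16-063, and do not present it as the long-term rate for the events in item 1.
3. State that M16-063 placebo time and events go to Placebo and not to ABBV-599 After Placebo. Use group names, since Group 7 is Placebo in SAP 6.0 but All ABBV-599 in 8.1.

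The cost is SAP wording and one extra table set; the exposure definition and the 30-day call already exist. The new rates rest on fewer patient-years, so intervals widen. With linear attrition and six equal groups, on-drug exposure per group is 110.4/6 = 18.4 to 147.2/6 = 24.5 PY.

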### **9.2.1 Treatment-Emergent Adverse Events**

To summarize data from Study M16-763 only, a treatment-emergent Adverse Event (TEAE) is defined as an adverse event with an onset date that is on or after the first dose of study drug from Study M16-763, and no more than 30 days after the last dose of study drug from Study M16-763.

To summarize a combination of data from Studies M16-063 and M16-763, a treatment-emergent Adverse Event (TEAE) is defined as an adverse event with an onset date that is on or after the first dose of study drug from Study M16-063, and no more than 30 days after the last dose of study drug from Study M16-763.

Events where the onset date is the same as Study M16-063 study drug start date are assumed to be treatment-emergent. If an incomplete onset date was collected for an adverse event, the event will be assumed to be treatment-emergent unless there is other evidence that confirms that the event was not treatment-emergent (e.g., the event end date was prior to the study drug start date).

The number and percentage of subjects experiencing TEAEs will be summarized.

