7.4 Statistical Analyses for Safety

All safety analyses will be performed in the Safety Analysis Set.

All treatment-emergent adverse events (TEAEs), SAEs, AEs leading to discontinuation, and AESI will be collected during the study. A TEAE is defined as an event with onset or worsening after the first study dose of study drug and within 30 days after the last dose of study drug administration. The number and percentages of subjects experiencing TEAEs will be tabulated using the Medical Dictionary for Drug Regulatory Activities (MedDRA®) system organ class and preferred term. Summaries (including percentages and event per 100 patient-year) of SAEs, deaths, AEs leading to discontinuation, and AESI will be provided as well. For selected laboratory and vital signs parameters, mean change from baseline and percentage of subject with evaluations meeting pre-defined criteria for Potentially Clinically Important values will be summarized.

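### SAP 9.2.1 defines a TEAE by onset date alone where protocol 7.4 also counts worsening, so an event that begins in M16-063 and worsens in the extension can be missing from the M16-763-only TEAE tables

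*SAP*

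**What the plan says.** Protocol 7.4: "A TEAE is defined as an event with onset or worsening after the first study dose of study drug", with a window that closes 30 days after the last dose. It does not say whether the first dose is that of M16-063 or of M16-763.

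SAP 9.2.1 gives two definitions. For the extension alone: "To summarize data from Study M16-763 only, a treatment-emergent Adverse Event (TEAE) is defined as an adverse event with an onset date" no earlier than the first M16-763 dose. For the two studies together, a TEAE is "an adverse event with an onset date that is on or after the first dose of study drug from Study M16-063". Both close 30 days after the last M16-763 dose, and neither mentions worsening. No other section of the SAP supplies a worsening rule. The SAP does not acknowledge the difference, although its version history (section 13.0) gives consistency with the protocol as one reason for the edits in version 2.0.

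On which tables use which definition, SAP 9.2 states: "TEAEs will be summarized using subject data from Study M16-763 and a combination of data from Studies M16-063 and M16-763". The event rates use the combined data alone: "Only the datasets from Studies M16-063 and M16-763 that includes any subject receiving a dose in Study M16-763 will be used for per 100" patient-years. The overview (9.2.2), SOC/PT (9.2.3), maximum severity (9.2.7) and maximum relationship (9.2.8) tables are all built on TEAEs. The overview uses the groups of SAP 6.0, which include both an ABBV-599-after-placebo group and a separate placebo group.

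**The concern.** In a rollover study, an AE can be open when the subject takes the first extension dose. If it was mild in M16-063 and becomes severe in the extension, the protocol's wording can make it an extension TEAE. The SAP's wording cannot, because the onset date is already fixed in the earlier study.

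Long-term safety is part of the primary objective, and the clinical hypothesis is that safety is maintained. Protocol 4.2 makes the main comparison one between the extension and the profile seen in each arm of the randomized study, so the extension-period count has to be right on its own. Leaving out worsening can only lower that count, which favours the hypothesis.

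The placebo-to-ABBV-599 subjects are the most exposed group. For them, a worsening after extension entry is a worsening after the first active dose.

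**Working it through.** The documents state no figure that depends on the TEAE definition, so there is nothing to recompute. The check is to classify each onset and worsening pattern under each rule. The protocol is read both ways because it does not name the study whose first dose it means.

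| Pattern | Protocol 7.4, M16-763 first dose meant | Protocol 7.4, M16-063 first dose meant | SAP, M16-763 only | SAP, combined |
|---|---|---|---|---|
| A. Onset on M16-063 treatment, worsens in extension, one AE record | TEAE (worsening) | TEAE (onset) | Not counted | Counted, at M16-063 onset |
| B. As A, but worsening entered as a new record | TEAE | TEAE | Counted | Counted |
| C. Onset before first M16-063 dose, worsens in extension, one record | TEAE (worsening) | TEAE (worsening) | Not counted | Not counted |
| D. Onset in extension | TEAE | TEAE | Counted | Counted |
| E. Incomplete onset date | Not addressed | Not addressed | Assumed TEAE unless evidence against | Assumed TEAE unless evidence against |

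What follows from the table:

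1. Pattern A is the main gap. It is confined to the M16-763-only tables, and pattern B closes it.
2. Pattern C is lost from both table sets, whichever first dose the protocol means. It may be the rarer case. Under this protocol's own collection rule (6.1), only SAEs and protocol-related non-serious AEs are gathered before dosing; the corresponding M16-063 rule is not in the documents.
3. Two SAP rules might seem to help but do not. The severity rule, "if the same adverse event occurs multiple times within a subject, the highest severity and level of relationship to investigational product will be reported", acts only on events already counted. The missing-date rule, "If an incomplete onset date was collected for an adverse event, the event will be assumed to be treatment-emergent", does nothing when the onset date is complete and falls before the first extension dose.
4. For a subject who moves from placebo to ABBV-599, pattern A is absent from the extension-only table and carries a placebo-period onset in the combined one. The SAP has no attribution rule, so the event could be tabulated under placebo and not under ABBV-599.

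**The case against.** A reader might infer that these events disappear from the extension's safety output altogether, and that severe, serious and discontinuation counts are understated throughout. The documents do not support that:

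- **Combined outputs.** The combined TEAE tables and the per-100-patient-year rates count any event with onset on M16-063 treatment. This stands. However, those outputs merge the two periods and keep the M16-063 onset, so they do not show that the worsening happened in the extension.
- **SAEs and discontinuations.** SAP 9.2.5 lists and tabulates SAEs and AEs leading to discontinuation without restricting them to treatment-emergent ones. This stands too. The overview, the SOC/PT tables and the listings in 9.2.11 do carry the restriction, and a severe but non-serious worsening that does not lead to discontinuation has no such backstop.
- **Laboratory changes.** A falling haemoglobin or rising transaminase appears in the shift, potentially-clinically-significant and liver-threshold summaries of SAP 9.3, whatever the AE onset date. This covers laboratory findings only.
- **Recording practice.** If each worsening becomes a new AE record, pattern A does not arise. The convention may be in the Operations Manual, whose text is not supplied, so its absence here is not evidence that it does not exist. The nearest protocol text (6.1) treats unexpected deterioration of a pre-existing condition as an AE, but only in connection with planned elective surgery. The loss is therefore conditional.
- **Which first dose.** If the protocol means the M16-063 dose, pattern A is already a TEAE by onset and the combined definition captures it. Pattern C is still lost, so the SAP is narrower on either reading.

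It is also tempting to put a number on the loss. The completion estimate implies about 200 subjects (40/0.20 = 120/0.60 = 200), but the documents give neither the share with an open AE at entry nor the share of those that worsen. Any count of affected subjects would rest on invented rates.

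**Conclusion.** The protocol and SAP definitions conflict, and the SAP does not justify the departure. As written, and provided a worsening stays on its existing AE record, the SAP omits from the M16-763-only overview, SOC/PT, severity and relationship tables an event that began in M16-063 and worsened in the extension. It omits from both table sets an event that predates the first M16-063 dose and worsened on treatment. The direction is known: TEAE counts can only be too low. The size is not derivable.

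The gap matters most for the placebo-to-ABBV-599 group and for the between-period comparison in protocol 4.2. It is worth correcting before database lock, but it does not mean that the extension's safety reporting as a whole is blind to these events.

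**What to change.** In SAP 9.2.1, extend both definitions so that a TEAE is an event whose onset, or whose increase in severity, falls on or after the first dose of the relevant period and within 30 days after the last dose. The relevant period starts with the first M16-763 dose for the extension-only tables and the first M16-063 dose for the combined tables. This brings the SAP into line with protocol 7.4.

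Add two supporting rules:

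- **Identification.** Worsening is taken from a new AE record or from a dated change in severity.
- **Attribution.** It is assigned to the treatment being taken when the event worsened, which is ABBV-599 for an extension worsening in Group 6. Because SAP 9.2.4 counts events and not subjects, say also whether a worsening adds to the event count.

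The cost is a small derivation step and slightly higher extension TEAE counts. The step needs the date of worsening. Neither document shows that the eCRF holds dated severity changes; if it keeps one severity per record, the recording convention has to be settled before the rule can be programmed. No new visits or assessments are needed.
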